### (iv) Cross-sector collaboration

This project will be undertaken by staff from two universities (Hong Kong Baptist University and Chinese University of Hong Kong), with close collaborations with local special schools. The project team leaders will oversee the whole study; the RA will be in charge of contacting with study schools, designing and implementing the programme, and preliminarily analysing the data; several student helpers will be responsible for pre- and post-intervention measurements and assist the PA during the implementation of the intervention.

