1. To reduce BMI among a sample of overweight and obese adolescent children with ID in local special schools;
2. To reduce % body fat among the sample;
3. To reduce waist-to-height ratio among the sample;
4. To reduce overweight and obese status among the sample;
5. To improve PA levels among the sample.

(d) Project Plan:

[figure not shown]
(i) Target group

The target population of the project will be adolescents with mild and moderate ID (aged 12- 18 years) who are overweight and obese. We will adopt a randomised controlled trial (RCT) design and recruit 64 overweight and obese students from 4-6 special schools, and then randomly and equally assign them into the intervention and control groups (32 in each group). This sample size can test an effect size of  $0.722 \text{ kg/m}^2$  (mean difference in change of BMI divided by pooled standard deviation), with an attrition rate of 20%. The selection criteria of participants include: (1) children with mild and moderate ID; (2) aged 13-18 years old; (3) being overweight or obese; (4) without physical disability; (5) without medical predispositions towards obesity (genetic syndrome or drug treatment) that could interfere with the results of the study; and (6) without contraindications for regular physical activity (e.g. asthma, heart disease). A written informed consent will be obtained from their parents/guardians in advance.

(ii) Implementation plan

*1. Description of intervention:*

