## 2. Description of control:

The participants in the control group will receive routine PE classes as usual during the intervention period (in the academic year of 2018/19).

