### (vi) Evaluation plan

#### 1. Outcome evaluation

Obesity-related indicators: obesity-related indicators include changes in BMI ( $\text{kg/m}^2$ , measured weight in kilograms divided by measured height in meters squared), waist circumference in centimeters, waist-to-height ratio (%), and % body fat. In addition, changes in body weight categories (such as changes from overweight/obesity to normal weight, changes from obesity to overweight or vice versa) will also be recorded, where the classification criteria using age- and gender-specific BMI cut-off points suggested by Cole will be adopted (Cole 2000).

Height will be measured to the nearest 0.1 cm using a stadiometer (Holtain Ltd., Pembrokeshire, United Kingdom). Weight will be measured to the nearest 0.1 kg on a digital balance scale (Seca, max. 200 kg, Germany) with the subject wearing lightweight clothing and no shoes. Then BMI will be calculated from weight and height. The waist circumference (in cm) will be measured midway between the lowest rib margin and the top of the iliac crest at the end of gentle expiration. The measure will be performed with a flexible meter ribbon accurate to 0.1 cm. The % body fat will be assessed by bio-impedance (Body stat 1500 MDD, Douglas, Isle of Man, United Kingdom).

All obesity-related indicators will be measured at the T1 (pre-intervention), T2 (end of Stage 1), T3 (end of Stage 2), and T4 (post-intervention) among all participants in the two groups.

***Heart rate measurements:*** HRrest of each participant will be measured at the beginning of each stage using the standard procedure. Participants will wear a Polar T31 Heart Rate Monitor (Polar Electro Inc., Lake Success, NY, USA) during HRrest measurement; their values will be averaged over the 20-min collection period. Exercise HR of each participant will be monitored using the Polar T31 during the instructional process following the standard procedure.

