This project will be undertaken by staff in Department of Physical Education, Hong Kong Baptist University (DPE) and JC School of Public Health and Primary Care, Chinese University of Hong Kong (SPHPC). The DPE has a long and proud history of its outstanding achievements across an array of academic fields related to physical education, sport and leisure services, whilst the SPHPC is made up of diverse professionals, such as health promotion specialists, epidemiologists, public health experts, and clinicians. Both of the two institutions will fully support this project. In addition, the team members from the both universities have been smoothly and successfully collaborating with each other on several studies in the past years. Last but not the least, The DPE holds two undergraduate programmes (AD and Top-up) with a focus on special population, through which it keeps a very close relationship with local special schools. Many schools receive our current students to fulfil their internship courses. A large portion of PE teachers are our alumnus. Taking our previous study as an example, we successfully invited more than one third of all special schools for children with mild and moderate ID into that study. Of the participating schools, three proactively asked if we could provide intervention programmes to them in future. Most schools gave positive answers when we asked the possibility to implement an intervention in their schools.

(f) Justification of Resource Requirements:

(i) Details

1. Research Assistant: A full-time project coordinator is needed to coordinate the data collection, implement the intervention, and assist in data analysis. A total cost of HK\$ 268200 was estimated according to our university's pay structure (HK\$14900/months for 18 months).
2. Payment to student helpers: we will need 4 student helpers in outcome measurements (height, weight, waist circumference, waist-to-height ratio, and % body fat) and implementation of the intervention. The hourly payment rate is HK\$49/hour, each student will work 10 months (at a rate of 1 hour/session, 2 sessions/week, and 4 weeks/months, totally 80 hours/student helper), generating a total cost of HK\$ 15680.

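### The four student helpers who assist the exercise sessions also take the outcome measurements, with no masking planned; this leaves the tape-read waist most open to bias, and a rota between schools would reduce it.

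*Combined protocol and SAP*

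**What the plan says.** Section 13(d)(iv), Cross-sector collaboration, states that "several student helpers will be responsible for pre- and post-intervention measurements and assist the PA during the implementation of the intervention". Section 13(f)(i), item 2, repeats the double role and names the outcomes: "we will need 4 student helpers in outcome measurements (height, weight, waist circumference, waist-to-height ratio, and % body fat) and implementation of the intervention".

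Section 13(d)(i) describes allocation of individual students: the project will "recruit 64 overweight and obese students from 4-6 special schools, and then randomly and equally assign them into the intervention and control groups". Under the description of control, the comparison group "will receive routine PE classes as usual during the intervention period".

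Section 13(d)(vi)1 sets four measurement times for both groups: "All obesity-related indicators will be measured at the T1 (pre-intervention), T2 (end of Stage 1), T3 (end of Stage 2), and T4 (post-intervention". Waist is taken midway between rib margin and iliac crest at the end of a gentle breath out, and "The measure will be performed with a flexible meter ribbon accurate to 0.1 cm". The documents do not mention masked or independent assessors, or say which helper measures at which school.

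**The concern.** Anyone assisting the twice-weekly sessions at a school sees which children attend. When the same person later takes a tape reading, knowledge of the group can move it in the expected direction through where the tape is placed, how tightly it is held and when it is read. Such a shift adds directly to the group difference. Randomisation does not remove it, and a larger sample makes a false rejection more likely, because a fixed bias is then estimated more precisely. Waist-to-height ratio is a stated objective (objective 3) and a listed outcome indicator, so a result there could reflect the measurer and not the programme.

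**Working it through.** The plan states no figure for assessor bias, so there is none to reproduce. The check reads the sections together and then sizes the risk under stated assumptions.

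**1. Does knowledge of the group follow?**
- The same four people assist and measure: 13(d)(iv) and 13(f)(i) agree.
- Allocation is by student, so both groups can be in one school (13(d)(i)).
- Controls have routine PE only, so attendance at sessions reveals the group.
- T1 precedes the sessions and is not affected by assisting them. T4 is affected, because 13(d)(iv) gives helpers the post-intervention measurement. T2 and T3 are affected if helpers also measure then, which the documents do not state.

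Knowledge of allocation is thus a strong inference, not a stated fact.

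**2. Which outcomes are exposed?**
- Waist: 1 cm of tape error moves waist-to-height ratio by 100/H percentage points. That is 100/170 = 0.59 to 100/150 = 0.67 for assumed heights of 170 and 150 cm.
- Height: over-reading by 1 cm lowers BMI by B × [1 − (H/(H+1))²]. For assumed BMI 25 at 170 cm this is 0.29 kg/m²; for BMI 30 at 150 cm it is 0.40 kg/m². Section 13(b)(ii) cites an effect of −0.35 kg/m² in overweight and obese children. A stadiometer leaves less room for judgement than a tape, so the risk is smaller.
- Weight (digital scale), % body fat (bio-impedance) and accelerometry leave the measurer little influence.

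**3. Size for waist.** Inputs from the plan: 32 per group, two-sided 0.05, 20% attrition (0.8 × 32 = 25.6, taken as 26). Assumed: SD of waist change 3-5 cm, shift of 0.25-1 cm in one group, simple two-sample t-test, no true effect.

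δ = shift/SD; λ = δ√(n/2); the false-positive rate is P(|T| > t₀.₉₇₅), with T non-central t on 2n − 2 df and non-centrality λ. Example: 1 cm with SD 5 cm gives δ = 0.20, λ = 0.20 × √16 = 0.80, rate 12.4%.

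| Shift | δ (SD 5 to 3 cm) | 32 per group | 26 per group |
|---|---|---|---|
| 0.25 cm | 0.05-0.083 | 5.4-6.2% | 5.4-6.0% |
| 0.5 cm | 0.10-0.167 | 6.8-10.1% | 6.4-9.1% |
| 1 cm | 0.20-0.333 | 12.4-25.9% | 10.9-21.8% |

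**4. Is there staff time for a rota?** The budget says "each student will work 10 months (at a rate of 1 hour/session, 2 sessions/week, and 4 weeks/months, totally 80 hours/student helper". 10 × 4 × 2 × 1 = 80 hours, and 4 × 80 × HK$49 = HK$15,680, as stated. If every helper attends all 72 sessions at the budgeted hour, 80 − 72 = 8 hours remain each, or 32 helper-hours in all. Four measurement times for 64 participants are 256 visits: 32 × 60/256 = 7.5 minutes each. If helpers measure only at T1 and T4, there are 128 visits, or 15 minutes each. Travel is budgeted at 72 trips per person for 4 persons, equal to the number of sessions, so separate measurement trips are not funded.

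**The case against.** The best reply is that the documents nowhere say helpers know a child's group when they measure. If each helper assists at one school, some readings may already be taken by someone who never saw that school's sessions. This stands as a limit on wording, but nothing in the plan secures that arrangement, and with four people in both jobs it would be left to chance.

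It can also be said that waist-to-height ratio is one of five objectives, that the site and breathing phase are specified, and that the sample size rests on BMI. All true, and this keeps the point modest. The t-test in the check is also simpler than the planned repeated-measures ANCOVA, so its rates show scale only.

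Several stronger readings are tempting and not supported:
- That helpers run the sessions. Section 13(d)(ii)1 gives delivery to the research assistant and PE teachers; helpers assist.
- That most positive waist findings could be spurious. An assumed 2 cm shift gives 35-75% with 32 per group (29-65% with 26), but the documents offer no basis for a shift of that size.
- That the research assistant, who delivers the programme and is charged with "preliminarily analysing the data", works on uncoded groups and decides how deviations are handled. The documents are silent on coding and do not give that discretion to the research assistant.
- That a swap would remove the problem. Children can still disclose their group.

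**Conclusion.** The point holds as a design weakness with an inexpensive improvement. The double role is explicit in two places and no masking offsets it. Later readings, certainly at T4, will very likely be taken with knowledge of the group wherever a helper measures at a school where he or she has assisted. The consequence is material mainly for waist and waist-to-height ratio.

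Its size depends wholly on assumptions, since the plan gives neither an SD of waist change nor a reading error. It is negligible at a 0.25 cm differential shift, modest at 0.5 cm, and serious at 1 cm, where the false-positive rate is two to five times the nominal level. The documents do not show that bias of any given size would occur.

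**What to change.** Before sessions begin, add to 13(d)(iv) and 13(d)(vi)1:
- Each helper assists sessions only at fixed, named schools. If helpers rotate through all schools, the next step fails.
- At T2-T4, each helper measures only at schools where he or she has not assisted. State who measures at T2 and T3.
- Measurers are not given the allocation list, and children and teachers are asked not to mention the group.

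No additional people are needed: there are four helpers and 4-6 schools, and both groups can be measured within a school. The costs are a rota, some travel beyond the 72 trips per person budgeted, and pressure on the helper hours shown above. If those limits bind, give priority to waist and height. Some disclosure by children will remain, and the change does nothing for the activity and eating habits reported by parents.

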### (v) Indicators and targets

Outcome indicators will consist of BMI, % body fat, waist-to-height ratio, body weight status, and PA levels. Taking BMI as an example, we expected to achieve an effect size of  $0.722 \text{ kg/m}^2$  (mean difference in change of BMI divided by pooled standard deviation) via the intervention.

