### (vii) Results analysis

IBM SPSS Statistics 23 will be used for data analysis. Continuous variables (e.g., BMI) will be presented with mean (standard deviation, SD) and/or median (interquartile rage, IQR) values. All continuous variables pre-intervention will be tested for between-group differences using independent sample t-test. Normality will be checked by QQ-plots, and tested for equal variance assessed by Levene's test. If skewed, the data will be logarithmically transformed before applying t-test.

A general linear model two-way repeated measure ANCOVA will be used to compare significant differences in the changes in the continuous outcome variables between the two groups, where group and time are the two factors of interest (Elmahgoub, 2011). Variables will be selected in a stepwise manner and only those with  $p < 0.1$  kept in the final models. A significance level of 0.05 will be adopted (two-tailed test). Intention-to-treat analysis will be adopted and performed to avoid bias from withdrawals or protocol deviations.

[Word Count: 2788 ]

(e) Existing Facilities:

We have all facilities needed in this project, including stadiometers, digital balance scales, Body stat 1500 MDD, Polar T31, ActiGraph accelerometers, questionnaires of subjective measurements of PA and eating habits.

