We expected that our programme, if effective, would be welcomed and adopted by other special schools to reduce obesity among their students in the future. We hold close collaborative relationship with many special schools, we have many alumnus working in the special schools, and we therefore could promote our programme via those links if it is effective. In addition, the effective model can also be extended to reach students with ID in normal schools. We will disseminate our findings by presenting on international conferences, publishing journal articles, and building up online platforms for learning and sharing to achieve as large benefits as possible. In the long run, we will equip our undergraduates with the effective APA programme, which they will bring to their receiving schools during internship and to their working schools after graduation.

(ii) How the project can be sustained after the funding period  
The APA programme will be designed and implemented by researchers and PE teachers together. If it is effective, the participating schools can independently run the APA programme after the funding period. Upon the completion of the project, we will building up and maintain online platforms via Facebook/Instagram with all deliverables generated from the project. The platforms can be accessed for free by teachers, parents, and other publics to learn and share experiences in obesity interventions. In addition, we will integrate the programme into our courses. Thus, our students can continue delivering the APA programme in the long run.

(h) Key References:

Commission on Youth, Hong Kong. (2014). Youth in Hong Kong: A Statistical Profile 2012. (Data is accessible on May 13, 2016 on <http://www.coy.gov.hk/en/research/index.html> ).

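### No primary outcome is named and effectiveness is left undefined, so the 5% level does not control the error of the trial's main conclusion

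*Combined protocol and SAP*

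**What the plan says.** The Executive Summary and section 13(c) list five objectives: BMI, % body fat, waist-to-height ratio, overweight and obese status, and physical activity (PA). They are numbered but not ranked.

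Section 13(d)(v) turns them into indicators: "Outcome indicators will consist of BMI, % body fat, waist-to-height ratio, body weight status, and PA levels". It then gives the only quantified target, introduced by "Taking BMI as an example". Section 13(d)(i) sizes the trial on the same standardised difference in BMI change, 0.722, without that qualifier.

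Section 13(d)(vi)1 says that "obesity-related indicators include changes in BMI" and goes on to "waist circumference in centimeters, waist-to-height ratio (%), and % body fat". Waist circumference is thus an outcome that appears in neither the objectives nor the indicator list. Measurements are taken at T1, T2, T3 and T4. Changes in weight category are to be recorded, with no test named.

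Section 13(d)(vii) specifies a two-way repeated-measures ANCOVA that "will be used to compare significant differences in the changes in the continuous outcome variables between the two groups". On the error level it says: "A significance level of 0.05 will be adopted (two-tailed test". It gives no multiplicity adjustment, testing order, key time point or key contrast.

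On use of the result, section 13(g)(i) says: "We expected that our programme, if effective, would be welcomed and adopted by other special schools". The Executive Summary (Deliverables) and 13(g)(ii) make continued running of the programme depend on the same condition. No section says which result would meet it.

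**The concern.** A two-sided level of 0.05 controls the error of one test. The plan runs that test on several outcomes and then draws one overall conclusion, that the programme is or is not effective. With no rule linking the two, the error rate of the conclusion is not the stated 5%.

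A mixed result is plausible in a trial of 64 adolescents with several overlapping measures of adiposity. If BMI did not differ but % body fat gave p < 0.05, the plan would offer no basis for saying whether the programme had worked. The choice would be made after the data were seen, and adoption by other schools would rest on it.

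The protocol's own usage shows how this could happen. Section 13(b)(iii) credits an earlier uncontrolled 9-month programme with reductions in waist circumference, waist-to-height ratio and % body fat; BMI is not in that list. Section 13(d)(ii)1 then cites the same study as showing that such a programme reduces obesity.

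**Working it through.** The plan states no family-wise error rate, so there is no figure of its own to reproduce.

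**Inputs from the documents**
- Level: two-sided 0.05 per outcome (13(d)(vii)).
- Outcomes clearly covered by the ANCOVA: BMI, waist circumference, waist-to-height ratio and % body fat, so k = 4. PA makes k = 5. PA is an objective and an indicator, but 13(d)(vi)1 assigns the accelerometer data to setting working loads and controlling confounding.
- Weight status is not counted, because no test is named for it.

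**Assumption.** The documents give no correlations between outcomes. I take an equal correlation r between test statistics and vary it from 0.5 to 0.9.

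**Step 1: independence, as an upper bound.** The chance of at least one p < 0.05 when there is no effect on anything is 1 − 0.95^k.
- k = 4: 1 − 0.95^4 = 0.185
- k = 5: 1 − 0.95^5 = 0.226

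Counting only results in favour of the intervention, it is 1 − 0.975^k.
- k = 4: 1 − 0.975^4 = 0.096
- k = 5: 1 − 0.975^5 = 0.119

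**Step 2: correlated outcomes.** Write each statistic as Z_j = √r·C + √(1−r)·E_j, with C and E_j independent standard normal and positive values favouring the intervention. The two-sided risk is 1 − P(all |Z_j| < 1.96). The favourable-direction risk is 1 − P(all Z_j < 1.96). Numerical integration over C gives the table below; for k = 5, simulation with 1,000,000 draws agrees.

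| r | k = 4, either direction | k = 5, either direction | k = 4, favourable only | k = 5, favourable only |
|---|---|---|---|---|
| 0.5 | 15.6% | 18.3% | 7.8% | 9.1% |
| 0.7 | 13.0% | 14.8% | 6.5% | 7.4% |
| 0.9 | 9.4% | 10.2% | 4.7% | 5.1% |
| Single test | 5% | 5% | 2.5% | 2.5% |

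The ratio to nominal runs from 9.4/5 = 1.9 to 18.3/5 = 3.7. The favourable-only columns give the same range: 4.7/2.5 = 1.9 to 9.1/2.5 = 3.6.

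**Step 3: sensitivity to the equal-correlation assumption.** PA may be less closely tied to the adiposity measures than they are to each other. With r = 0.5 to 0.9 among the four adiposity measures and 0.2 with PA (both assumed), the risk for k = 5 is 19.6% down to 13.8% in either direction, and 9.9% down to 6.9% in the favourable direction.

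**Step 4: what co-equal outcomes would cost.** Bonferroni for five outcomes gives a level of 0.05/5 = 0.01. For a standardised difference of 0.722 in a two-sample t-test:
- 32 per group: power 81% at 0.05, 59% at 0.01.
- 0.8 × 32 = 25.6 per group after the plan's 20% attrition: 72% at 0.05, 47% at 0.01.
- 80% power (assumed; the plan states none) at 0.01: 47 evaluable per group, 47/0.8 = 58.75, so 59 per group and 118 in total.

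**The case against.** The strongest defence is that BMI is already the lead outcome in all but name. It is objective 1, it comes first in both outcome lists, and it alone has a target and a sample size. The sizing statement in 13(d)(i) is not qualified as an example; that phrase occurs only in 13(d)(v). This stands as far as it goes: the gap could be closed with a label. But being first and being sized is not a commitment to judge the trial on BMI, and 13(d)(v) presents BMI as an illustration.

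A reader might also draw four stronger conclusions that the documents do not support.
- **That the plan lets any one significant indicator count as success.** No section says so. The fault is that no rule exists.
- **That the false-positive risk is 23% to 26%.** Those are independence values for five and six tests, counted in both directions. Waist-to-height ratio is waist circumference divided by height, and weight status is derived from BMI cut-offs, so independence cannot hold. A false claim of benefit also needs a result in the favourable direction.
- **That six outcomes are tested.** A sixth test would be one of weight status, and the plan names none. With PA's mixed role, four or five is the supportable count.
- **That four visits multiply the tests.** A repeated-measures model can give one group-by-time test per outcome, and no visit-by-visit testing is specified.

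**Conclusion.** The point holds in this limited form. No outcome is named primary, the continuous outcomes are all tested at two-sided 0.05 without adjustment or order, and effectiveness is undefined. If a result on a single indicator were reported as effectiveness, the error rate would be roughly two to four times nominal: about 9% to 18% against 5% in either direction, or about 5% to 9% against 2.5% in favour of the intervention. The independence values for either direction, 19% to 23%, are upper bounds.

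These figures assume four or five tested outcomes, no effect on any of them, and equal correlations of 0.5 to 0.9 that the documents do not supply. They leave out two further sources of flexibility that I have not quantified: two analysis sets (exclusion below 80% attendance in 13(d)(iii), and intention-to-treat), and stepwise variable selection at p < 0.1 in 13(d)(vii). The opening pages were not available to check.

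This should be corrected before analysis. It does not make the trial unworkable.

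**What to change.** State in 13(d)(v) and 13(d)(vii) that:
- change in BMI from T1 to T4 is the single primary outcome;
- it is tested by the T4 between-group contrast from the planned repeated-measures model, in the intention-to-treat population, at two-sided 0.05;
- *effective*, wherever it governs roll-out, means that this test is significant in favour of the intervention;
- % body fat, waist-to-height ratio, waist circumference, weight status and PA are secondary, reported with 95% confidence intervals and either Holm-adjusted or labelled supportive.

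Naming the contrast matters because a test of T1-to-T4 change is not the same as an overall group-by-time test across four visits. The covariates for this contrast should also be fixed in advance, since data-driven selection would leave the 5% unsecured.

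The cost is a few sentences of text and no additional participants, because the trial is already sized on BMI change. The price is that a result on a secondary outcome alone can no longer be called proof of effectiveness. Keeping five co-equal outcomes under Bonferroni would cost far more, as Step 4 of the working shows.
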